7.4.1.2. Method of Detecting AEs and SAEs

Care will be taken not to introduce bias when detecting AEs and/or SAEs. Open-ended and non-leading verbal questioning of the subject is the preferred method to inquire about AE occurrence. Appropriate questions include:

- “How are you feeling?”
- “Have you had any (other) medical problems since your last visit/contact?”
- “Have you taken any new medicines, other than those provided in this study, since your last visit/contact?”

7.4.1.3. Follow-up of AEs and SAEs

After the initial AE/SAE report, the investigator is required to proactively follow each subject at subsequent visits/contacts. All SAEs and non-serious AEs of special interest (as defined in Section 7.4.1.4) will be followed until resolution, until the condition stabilizes, until the event is otherwise explained, or until the subject is lost to follow-up

(as defined in Section 5.4.1). Further information on follow-up procedures is given in [Appendix 7](#).

7.4.1.4. Adverse Events of Special Interest

A number of adverse events of special interest have been identified as part of the risk assessment outlined in Section 4.7.1 due to the co-administration of two biologics and will be monitored for the duration of the study. These AESIs include infections (including opportunistic), systemic infusion / injection reactions, hypersensitivity reactions, malignancy, psychiatric events (including suicidality), severe skin reactions (including Toxic Epidermal Necrolysis and Stevens-Johnson syndrome), immunogenicity, cardiac disorders, posterior reversible encephalopathy syndrome (PRES), PML, and AE's related to the biopsy procedure. The analyses of these events will be described in the Reporting and Analysis Plan.

7.4.1.5. Cardiovascular and Death Events

For any cardiovascular events detailed in [Appendix 7](#) and all deaths, whether or not they are considered SAEs, specific Cardiovascular (CV) and Death sections of the eCRF will be required to be completed. These sections include questions regarding cardiovascular (including sudden cardiac death) and non-cardiovascular death.

The CV eCRFs are presented as queries in response to reporting of certain CV MedDRA terms. The CV information should be recorded in the specific cardiovascular section of the eCRF within one week of receipt of a CV Event data query prompting its completion.

The Death eCRF is provided immediately after the occurrence or outcome of death is reported. Initial and follow-up reports regarding death must be completed within one week of when the death is reported.

7.4.1.6. Regulatory Reporting Requirements for SAEs

Prompt notification by the investigator to GSK of SAEs related to study treatment is essential so that legal obligations and ethical responsibilities towards the safety of subjects and the safety of a product under clinical investigation are met.

GSK has a legal responsibility to notify both the local regulatory authority and other regulatory agencies about the safety of a product under clinical investigation. GSK will comply with country specific regulatory requirements relating to safety reporting to the regulatory authority, Institutional Review Board (IRB)/Independent Ethics Committee (IEC) and investigators.

Investigator safety reports are prepared for suspected unexpected serious adverse reactions according to local regulatory requirements and GSK policy and are forwarded to investigators as necessary.

An investigator who receives an investigator safety report describing a SAE(s) or other specific safety information (e.g., summary or listing of SAEs) from GSK will file it with the IB and will notify the IRB/IEC, if appropriate according to local requirements.

7.4.2. Pregnancy

- Pregnancy testing and contraception are required until 16 weeks post last administration of study treatment for those subjects who complete Weeks 46-52 or withdraw from treatment prior to Week 8 dosing. Pregnancy testing and contraception are required for approximately 12 months after the administration of the final rituximab/placebo dose for the subset of subjects who discontinue treatment from Week 8 up to Week 46.
- Details of all pregnancies in female subjects will be collected for pregnancies occurring after the start of dosing and until either (a) 16 weeks post last administration of study treatment for those who complete Weeks 46-52 or withdraw from treatment prior to Week 8 dosing or (b) 12 months after the last administration of rituximab/placebo for subjects who discontinue treatment from Week 8 up to Week 46.
- If a pregnancy is reported, then the investigator should inform GSK within 2 weeks of learning of the pregnancy and should follow the procedures as outlined in [Appendix 8](#).
- Women who become pregnant while on active treatment will be withdrawn from therapy but will continue in the trial for safety reporting and outcomes assessments. The pregnancy must be followed up to determine outcome (including premature termination), and status of mother and child including a one-year pediatric follow-up.

7.4.3. Physical Exams

- A complete physical examination will include, at a minimum, assessment of the Head and Neck, Skin, Cardiovascular, Respiratory, Gastrointestinal, Musculoskeletal and Neurological systems. Height and weight will also be measured and recorded.
- An abbreviated physical examination will include, at a minimum, assessments of the eyes, mouth, skin, joints, lungs, cardiovascular system, and abdomen (liver and spleen).
- Investigators should pay special attention to clinical signs related to previous serious illnesses.
- A questionnaire-based neurological examination to detect any signs or symptoms consistent with the diagnosis of PML will be conducted at each visit. The questionnaire is shown in [Appendix 5](#). If any question is answered ‘yes’ and the reason for the symptom is unknown (i.e., is not definitively explained by other known cause), the subject will be referred to a neurologist for evaluation. An MRI with gadolinium enhancement (pending renal function evaluation) and/or Cerebrospinal Fluid (CSF) JCV PCR are recommended to be performed to confirm the diagnosis. In addition, the investigator should contact the Medical Monitor within 2 business days if any question is answered ‘yes,’ regardless of suspected cause, to discuss appropriate management of the patient. Any findings should be reported as an adverse event and the PML reporting procedures followed, as in Section [7.4.7](#). A PML Adjudication Committee will review all cases of PML and suspected PML, and will provide their opinion to the sponsor.

7.4.4. Vital Signs

- Vital signs will be measured in semi-supine position after 5 minutes rest and will include temperature, systolic and diastolic blood pressure, pulse rate and respiratory rate.
- Three readings of blood pressure and pulse rate will be taken.
- First reading should be rejected.
- Second and third readings should be averaged to give the measurement to be recorded in the eCRF.

7.4.5. Electrocardiogram (ECG)

- 12-lead ECGs will be obtained at screening. If the ECG demonstrates a QTcB or QTcF interval ≥ 450 msec (≥ 480 msec for subjects with a Bundle Branch Block), there is a requirement to obtain two additional, consecutive ECGs (for a total of three). The investigator will then average the three QTc (and QT) intervals obtained and document the following from the 1st ECG:
 - Rate
 - PR interval
 - QRS axis

7.4.6. Clinical Safety Laboratory Assessments

All protocol required laboratory assessments, as defined in the Time and Events Table (in Section 7.1) must be conducted in accordance with the Laboratory Manual and Protocol Time and Events Schedule. Laboratory requisition forms must be completed and samples must be clearly labeled with the subject number, protocol number, site/center number, and visit date. Details for the preparation and shipment of samples will be provided by the laboratory and will be detailed in the SRM or the laboratory manual. Reference ranges for all safety parameters will be provided to the site by the laboratory responsible for the assessments.

If additional, non-protocol specified laboratory assessments are performed at the institution's local laboratory and result in a change in subject management or are considered clinically significant by the investigator (e.g., SAE or AE) the results must be recorded in the eCRF.

Refer to the SRM for appropriate processing and handling of samples to avoid duplicate and/or additional blood draws.

NOTE: Local laboratory results are only required in the event that the central laboratory results are not available in time for either a treatment and/or response evaluation to be performed. If a local sample is required, it is important that the sample for central analysis is obtained at the same time. Additionally, if the local laboratory results are used

to make either a treatment or response evaluation, the results must be entered into the eCRF.

Hematology, clinical chemistry, urinalysis and additional parameters to be tested are listed in [Table 1](#).

Table 1 Protocol Required Safety Laboratory Assessments

Laboratory Assessments	Parameters			
Hematology	CBC:		RBC Indices:	
	WBC Count		RBC Count	
	Hemoglobin		MCV	
	Hematocrit		MCH	
	Platelet Count		Monocytes	
			Eosinophils	
		Basophils		
Clinical Chemistry	Sodium	Chloride	BUN	Glucose
	Potassium	Bicarbonate	Creatinine	Calcium
	Total and direct bilirubin	ALT (SGPT)	AST (SGOT)	Alkaline phosphatase
	Total Protein	Albumin	Creatine Kinase	Uric acid
Routine Urinalysis	
 Specific gravity pH, glucose, protein, blood and ketones by dipstick 
 Microscopic examination (if blood observed or protein is abnormal) Urine protein quantitative analysis (if indicated) 			
Additional safety tests	
 IgG, IgM, IgA. CD19 B cell counts, CD4 & CD8 cell counts 			
Other Screening Tests	
 HIV, Hepatitis B (HBsAg) and HbcAb Hepatitis C (Hep C antibody) FSH and estradiol (as needed in women of non-child bearing potential only) Serum or urine hCG Pregnancy test (as needed for women of child bearing potential)² 			
NOTES:	
Details of Liver Chemistry Stopping Criteria and Required Actions and Follow-Up Assessments after liver stopping or monitoring event are given in Section 5.4.5 and Appendix 2.
 
Local urine testing will be standard for the protocol unless serum testing is required by local regulation or ethics committee.
			

With the exception of CD19+ B-cell levels (see “Follow up period” in Section [4.3](#)), all laboratory tests with values that are considered clinically significantly abnormal during participation in the study or within 30 days after the last dose of study treatment should be repeated until the values return to normal or baseline. If such values do not return to normal within a period judged reasonable by the investigator, the etiology should be identified and the sponsor notified.

7.4.7. **Progressive Multifocal Leukoencephalopathy (PML)**

Progressive multifocal leukoencephalopathy (PML) is a rare demyelinating infection of the CNS caused by initial infection or reactivation of the John Cunningham virus (JCV). Asymptomatic primary infection with JCV typically occurs in childhood with latent virus remaining dormant in the kidneys and lymphoid organs. In the context of immunosuppression, the virus can reactivate and involve the brain. Prior to 2000, most cases of PML had a fatal outcome. PML has been recently associated with immunosuppressive therapy, notably natalizumab, rituximab, efalizumab, mycophenolate mofetil, and tacrolimus [Schmedt, 2012].

In order to accommodate potential development of PML, neurological examinations will be conducted at the time points indicated in Section 7.1, the Time and Events Table.

Signs and symptoms of PML include visual disturbances, ocular movements, ataxia, and changes in mental status such as disorientation or confusion. These symptoms are not an exhaustive list and the investigator should exercise judgment in deciding to report signs and symptoms to sponsor promptly.

If a subject develops neurological signs or symptoms consistent with PML, treatment with investigational product should be halted and the subject referred to a neurologist or PML specialist for evaluation. Neurological evaluation for PML should focus on clinical symptoms, imaging studies and evidence of the virus in the CSF. The PML algorithm should be followed for all suspected cases of PML (See [Appendix 4](#)).

If the assessments are positive, the patient should proceed to the Follow-Up Period. All such patients will be followed until resolution. Any patient with a diagnosis of PML will be withdrawn from IP.

An independent PML Adjudication Committee will be utilized in this study to confirm any PML events. The PML Adjudication Committee will review blinded data for any subject with suspected PML and report the outcome of their adjudication review to the sponsor.

Note: The GSK Medical Monitor must be informed **within 2 business days** in the event a subject is identified as having neurological signs and symptoms suggestive of a diagnosis of PML. If PML is not confirmed, the investigator will inform the Medical Monitor of the relevant diagnosis and any action taken.

Refer to the SRM for further information and detailed guidance for completing and transmitting these and other SAE reports for patients who experience a serious infection, malignancy, death, sign or symptom of PML.

The investigator will do the following when reporting a serious infection (including PML) or sign/symptom consistent with PML.

Promptly report the event, as with any other SAE, as per Section 7.4.1.

Provide key source documentation for the Sponsor to assist with the safety evaluation process.

Examples of key source documents include but are not limited to: hospitalization records, discharge summaries, laboratory evaluations, biopsy results, culture/sensitivity results, death certificates, and autopsy reports.

If the patient has not otherwise been withdrawn from the study, then the investigator should contact the Sponsor to discuss the appropriate course of action regarding study continuation.

7.4.8. Suicidal Risk Monitoring

Some autoimmune diseases have an increased risk of suicidal behavior and/or ideation [Bachen, 2009; Timonen, 2003; Stenager, 1992]. For this reason, in studies of patients with autoimmune disease, patients should be clinically assessed for suicidal ideation and/or behavior at each visit. In this study, the Columbia Suicidality Severity Rating Scale (C-SSRS (www.cssrs.columbia.edu) will be used to assess suicidal ideation and behavior. It is recommended that the Investigator consider mental health consultation or referral for subjects who experience signs of suicidal ideation or behavior. The Medical Monitor should be notified when these events occur. In addition, a “yes” to any suicidal behavior or ideation question on the C-SSRS prompts the completion of the Possible Suicidality Related Adverse Event Questionnaire (PSRAE) Details of the C-SSRS and PSRAE questionnaires will be provided in the SRM.

7.5. Pharmacokinetics

All randomized subjects will be sampled for serum belimumab and rituximab levels. Assessment of belimumab and rituximab concentrations will be performed at the time points indicated in Section 7.1, Time and Events Table. Details of blood sample collection (including volume to be collected), processing, storage and shipping procedures are provided in the SRM.

7.6. Biomarker(s)/Pharmacodynamic Markers

Samples for biomarkers and pharmacodynamic markers will be collected as indicated in Section 7.1, Time and Events Table.

The timing of collections may be adjusted based on emerging PK or PD data from this study or other information in order to ensure optimal evaluation of the PD endpoint.

Details of blood sample collection (including volume to be collected), processing, and storage will be provided in the SRM.

All samples will be retained for a maximum of 15 years after the last subject completes the trial.

7.6.1. Novel Biomarkers

A secondary endpoint will be the quantification of B cells, such as a change in B/T cell ratio measured by immunohistochemistry (IHC) analysis of B and T cell numbers within lymphoid foci in the salivary gland as assessed at Day 0 and Week 24 and as described in Section 7.6.1.1.

An exploratory endpoint is to identify other mechanistic measures that may be more sensitive in detecting the effects of, or may provide more insight into, the effect of the co-administration treatment on the immune system and is described in Section 7.6.1.1 through Section 7.6.1.4. For all Biomarkers/PD assays and procedures, further details are provided in the SRM. Details of the analyses performed can be found in the RAP.

7.6.1.1. Assessment of the Salivary Gland Cellular Composition

Histological analysis of biopsy samples will include assessment of lymphocyte infiltrate, B cell and T cell subsets assessed through analysis of foci scoring, and IHC. IHC assessments may include B cell markers: CD20, IgG, IgM, IgA and CD38; T cell markers: CD3, markers of germinal center formation, CD21 and markers of dividing cells, Ki67. Changes in lymphocytes populations in glandular tissue may be further evaluated using epigenetic quantification or other equivalent technology and/or additional IHC markers of leukocyte infiltration and activation and/or glandular biology. Sections of salivary gland will be assessed by a pathologist to score glandular pathology.

7.6.1.2. Peripheral Blood Leukocyte Analysis

B cell flow cytometry panels will be used to measure changes over the course of therapy in the transitional, naive, memory and plasma B cell compartments. For subsets of interest, absolute numbers of cells and proportions relative to all B cells will be determined as well as activation status.

Peripheral blood mononuclear cells (PBMCs) may be collected and stored to allow for further evaluation of leukocyte populations to further support mechanistic understanding of treatment.

7.6.1.3. Serological Biomarkers

The quantification of serum analytes, autoantibodies [including anti-SSA and SSB], markers of B cells activation [may include but not limited to Beta-microglobulin, free kappa and lambda light chain], cytokines [may include but not limited to BLyS, IL-6, IL-21], chemokines [may include but not limited to CXCL13 and CCL19] and other analytes associated with immune activation [may include but not limited to complement C3, C4, and CH50] or Sjögren's biology will be performed using Luminex, ELISA or other appropriate technologies on serum or other assay appropriate blood matrix. Serum may be further analyzed for novel biomarkers and correlation with transcriptomic analysis of blood and glandular tissue. Serum for longitudinal analysis will be collected and stored for analysis at the end of the study.

7.6.1.4. Additional Exploratory Biomarkers

7.6.1.4.1. *Saliva Proteomics*

Saliva may be analyzed for novel biomarkers and correlation with transcriptomic and serologic analysis of blood and glandular tissue. Saliva for longitudinal analysis will be collected and stored as described in the SRM and may be analyzed at the end of the study.

7.6.1.4.2. *Transcriptomic Analysis*

Transcriptome studies on blood and salivary gland tissue may be conducted using microarray and/or alternative equivalent technologies including RNA sequencing (RNA-seq), which facilitates the simultaneous measurement of the relative abundance of thousands of RNA species, resulting in a transcriptomic profile for each blood and glandular sample. This will enable the evaluation of the changes in transcripts relevant to leukocyte activation, cellular composition and ectopic lymphoid structure development.

7.6.1.4.3. *B and T Cell Receptor Clonal Analysis*

An additional analysis of the effect of treatment on B and T antigen receptor clonal usage may be performed to assess the degree of expansion of B and T subpopulations in the blood and salivary gland tissue and the effect of treatment on expanded populations.

7.6.1.5. Immunogenicity

Serum samples will be collected for belimumab and rituximab immunogenicity assessment prior to dosing and after treatment start as indicated in Section 7.1, Time and Events Table.

7.7. Genetics

Information regarding genetic research is included in [Appendix 6](#).

8. DATA MANAGEMENT

For this study, subject data will be entered into GSK defined electronic case report forms (eCRFs), transmitted electronically to GSK or designee and combined with data provided from other sources in a validated data system.

Management of clinical data will be performed in accordance with applicable GSK standards and data cleaning procedures to ensure the integrity of the data, e.g., removing errors and inconsistencies in the data. Adverse events and concomitant medications terms will be coded using MedDRA (Medical Dictionary for Regulatory Activities) and an internal validated medication dictionary, GSKDrug. eCRFs (including queries and audit trails) will be retained by GSK, and copies will be sent to the investigator to maintain as the investigator copy. In all cases, subject initials will not be collected or transmitted to GSK according to GSK policy.

9. STATISTICAL CONSIDERATIONS AND DATA ANALYSES

9.1. Hypotheses and Treatment Comparisons

The primary objective of the study is to investigate the safety and tolerability of the co-administration of belimumab with rituximab and belimumab monotherapy. No formal statistical comparisons will be conducted to assess this objective.

Secondary efficacy and mechanistic endpoints will be investigated. The following exploratory comparisons may be conducted:

- Co-administration belimumab/rituximab treatment arm vs. Placebo arm
- Co-administration belimumab/rituximab treatment arm vs. Rituximab monotherapy arm
- Co-administration belimumab/rituximab treatment arm vs. Belimumab monotherapy arm
- Belimumab monotherapy arm vs. Placebo arm
- Belimumab monotherapy arm vs. Rituximab monotherapy arm

If deemed appropriate, these exploratory comparisons will be made investigating ESSDAI, stimulated salivary flow, oral dryness numeric response scale and a subset of salivary gland and plasma B cell parameters. Full details will be included in the RAP.

For all other parameters, no formal statistical comparisons will be made, although trends over time will be investigated across all treatment arms.

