2. INTRODUCTION

2.1. Study Rationale

Primary Sjögren's syndrome (pSS) is a common autoimmune disease characterized by oral and ocular dryness as well as systemic manifestations. B cells are thought to play a central pathogenic role. There are no disease modifying treatments for this disease and existing approved therapies consist of symptomatic treatments that do not address the autoimmune pathology. Therefore, substantial unmet medical need exists for a disease modifying therapy; one that can stop B-cell mediated autoimmune damage, alleviate glandular as well as constitutional symptoms and ameliorate extra-glandular target organ manifestations.

Clinical studies suggest that targeting B-cells with belimumab or rituximab may improve disease symptoms of patients with Sjögren's syndrome. In addition, scientific evidence suggests that dual B-cell targeted immunotherapy with both B lymphocyte stimulator (BLyS) blockade (i.e., belimumab) and B cell depletion (i.e., rituximab) may be more efficacious than targeting either mechanism alone. Therefore, this proof of mechanism study will assess whether either dual B-cell immunotherapy (i.e., co-administration of belimumab and rituximab) or belimumab monotherapy demonstrates a favorable safety and tolerability profile and results in improvements in clinical status, functional outcomes and mechanistic endpoints in comparison to placebo or rituximab monotherapy.

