3. OBJECTIVES AND ENDPOINTS

Objectives	Endpoints
Primary	

 Safety and tolerability of anti-BLyS / anti-CD 20 co-administration therapy and anti-BLyS and anti-CD 20 monotherapies 	
 Safety and tolerability; including incidence of SAEs and AESIs.
Secondary	

 Clinical efficacy of anti-BLyS / anti-CD 20 co-administration therapy and anti-BLyS and anti-CD 20 monotherapies Assessment of anti-BLyS / anti-CD 20 co-administration therapy and anti-BLyS and anti-CD 20 monotherapies on tissue B-cells. 	
 ESSDAI score over time Stimulated salivary flow over time Oral dryness numeric response scale over time B cell quantification within salivary gland biopsy at Week 24

Objectives	Endpoints
Exploratory 
 Assessment of mechanism and durability of effect of anti-BLyS/anti-CD 20 co-administration therapy and anti-BLyS and anti-CD20 monotherapies. 	
 Ocular dryness numeric response scale over time Lacrimal gland function as measured by Schirmer's test. Physician's Global Assessment (PGA) of disease activity over time Serologic markers over time Change in peripheral blood leukocytes including B cell subsets over time BLyS levels in blood Immunogenicity of rituximab and belimumab Pharmacokinetics of rituximab and belimumab Change from baseline in the cellular composition of the salivary gland Sustained efficacy of anti-BLyS/anti-CD 20 co-administration at Week 52 Additional exploratory biomarkers may be evaluated 
 Transcriptomic analysis of blood and salivary gland B and T cell receptor clonal analysis in peripheral blood and salivary gland Proteomic assessment of the saliva
Health Outcomes 
 Gather preliminary information on patient reported outcomes of anti-BLyS/anti-CD 20 co-administration therapy and anti-BLyS and anti-CD 20 monotherapies 	
 ESSPRI score (and individual scale subscores) over time Fatigue and Discomfort- SICCA Symptom Inventory (PROFAD SSI SF) over time Patient Global Assessment (PtGA) of disease activity over time Subject exit interviews

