9.2.1. Sample Size Assumptions

The study is not powered to detect pre-defined differences. Initially, approximately 70 subjects will be recruited.

Following interim analysis the number of subjects in some or all treatment arms may be increased following sample size re-estimation, up to a maximum of 120 total subjects in the study where up to a maximum of 25, 45, 30 and 20 will be randomized to placebo, belimumab monotherapy, co-administration therapy and rituximab monotherapy, respectively. This will be dependent on variability and placebo rates for certain parameters. More details will be included in the RAP.

The primary objective of the study is safety, where a number of safety events are of interest. Using a Bayesian approach to determine the confidence interval around an observed safety event in the co-administration group, we would have a flat Beta(1,1)

prior, and if we were to observe 1 safety event in 20 then the posterior distribution would be Beta (2,20), as outlined below:

We can be 95% certain that the true probability of the safety event lies between 0.01 and 0.24.

For supportive information, with 20 patients randomized to belimumab or the belimumab / rituximab arm and 10 to placebo, the smallest difference in ESSDAI between the two treatment groups that would be statistically significant would be -3.30, assuming a placebo change from baseline of -1.7 [TEARS, [Devauchelle-Pensec](#), 2014], a standard deviation of 4.192 [BELISS, [Mariette](#), 2015] and alpha=5%.

Following the interim analysis, if the number of subjects were to increase to those outlined above then the following would apply for the continuous ESSDAI score, assuming a placebo change from baseline of -1.7 [TEARS, [Devauchelle-Pensec](#), 2014], a standard deviation of 4.192 [BELISS, [Mariette](#), 2015] and alpha=5%:

Placebo	Active	Difference	Placebo N	Active N	Power to detect difference
-1.7	-4.7	3	25	45	82%
-1.7	-4.7	3	25	40	80%
-1.7	-4.7	3	25	35	78%
-1.7	-4.7	3	25	30	75%

For responder endpoints, including the proportion of patients who achieve a 30% improvement in oral dryness response scale; or the proportion of patients who achieve a 30% improvement in stimulated salivary flow, then the smallest difference between the 2 treatment groups that would be statistically significant is 33%, assuming a placebo response of 14%, for example.

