9.4.2. Analysis of Primary Endpoints

No formal statistical testing will be performed on safety data.

All safety evaluations will be based on the safety population. Clinical interpretation will be based upon review and displays of AEs, laboratory values and vital signs. The principle consideration in this evaluation will be the investigator-reported relationships of either AEs or laboratory abnormalities to IP.

Safety data will be presented in tabular and/or graphical format.

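### Safety is the primary objective, yet the protocol excludes formal between-arm comparison and quantifies precision for one arm only, so the risk added by co-administration gets no interval

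*Protocol*

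**What the plan says.** Section 3 gives the primary objective as "Safety and tolerability of anti-BLyS / anti-CD 20 co-administration therapy and anti-BLyS and anti-CD 20 monotherapies". Section 9.1 words it more narrowly: "The primary objective of the study is to investigate the safety and tolerability of the co-administration of belimumab with rituximab and belimumab monotherapy". The synopsis analysis text has the same narrower scope, so rituximab monotherapy drops out in both places.

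Section 9.1 then says "No formal statistical comparisons will be conducted to assess this objective", and Section 9.4.2 says "No formal statistical testing will be performed on safety data". Section 9.4.2 plans displays of adverse events, laboratory values and vital signs, and takes the investigator-reported relationship to study treatment as its main consideration. Under Section 6.3 those investigators are blinded to arm.

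The sample-size section quantifies safety precision for co-administration only. For 1 event in 20 it says "We can be 95% certain that the true probability of the safety event lies between 0.01 and 0.24", and the table in Section 9.2.2 repeats this for smaller numbers of completers. Section 9.4.3, by contrast, gives ESSDAI, stimulated salivary flow and oral dryness point estimates and 95% intervals for the between-arm comparisons listed in Section 9.1.

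**The concern.** The safety worry in Section 4.7 is incremental. It lists risks that co-administration might increase, and it judges the small prior experience by whether anything appeared beyond what either agent alone would produce. The randomised contrast with rituximab addresses that directly, and Section 4.2 gives the two arms about 20 subjects each.

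Neither of the two tools the protocol specifies does the same job. A one-arm interval needs an outside background rate, and the protocol's own background can be very wide: Section 4.7.1 puts serum sickness with rituximab in this disease at 6 to 38%. Attribution by an investigator who does not know the arm cannot separate combination risk from rituximab risk.

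At stake is whether a reader of the primary result can see how much added risk the data leave open. As written, three secondary endpoints get between-arm estimates with intervals and the primary objective does not.

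**Working it through.** **Inputs.** Arm sizes are co-administration 20, rituximab 20, belimumab 20 and placebo 10 (Section 4.2), with a Beta(1,1) prior (Section 9.2.1). The event counts below are illustrative assumptions, apart from the protocol's own 1 in 20.

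**1. The protocol's figure.** After 1 event in 20 the posterior is Beta(1+1, 1+19) = Beta(2,20). Its 2.5% and 97.5% points are 0.0117 and 0.2382, so the stated 0.01 to 0.24 reproduces. It describes one arm.

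**2. Difference interval, Newcombe.** With Wilson limits (l, u) for each arm and d = p1 - p2:

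- lower = d - sqrt[(p1 - l1)² + (u2 - p2)²]
- upper = d + sqrt[(u1 - p1)² + (p2 - l2)²]

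For 1/20 v 1/20, p = 0.05 and the Wilson limits are 0.0089 and 0.2361 in both arms. The half-width is sqrt[(0.2361 - 0.05)² + (0.05 - 0.0089)²] = sqrt[0.0346 + 0.0017] = 0.191, so the difference is 0 with limits -19 to +19 points.

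**3. Difference interval, Bayesian.** Independent Beta(1+x, 1+n-x) posteriors, difference taken over 2 million draws. For 1/20 v 1/20 this gives -17 to +17 points.

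**4. Other counts (percentage points, co-administration minus comparator).**

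| Events | Difference | Newcombe 95% | Beta(1,1) 95% |
|---|---|---|---|
| 0/20 v 0/20 | 0 | -16 to +16 | -13 to +13 |
| 1/20 v 1/20 | 0 | -19 to +19 | -17 to +17 |
| 2/20 v 2/20 | 0 | -21 to +21 | -20 to +20 |
| 3/20 v 3/20 | 0 | -23 to +23 | -23 to +23 |
| 4/20 v 1/20 | +15 | -7 to +37 | -7 to +35 |
| 1/20 v 0/10 (placebo) | +5 | -23 to +24 | -21 to +19 |

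At 20 v 20, equal counts of 0 to 3 leave an excess of about 13 to 23 points open, depending on count and method. At the maximum sizes in Section 9.2.1, 3/30 v 2/20 (rituximab) still gives 0 with Newcombe limits -21 to +17.

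**5. Why intervals and not tests.** The protocol gives no comparator rates for these arms, so the following rates are assumed. At 20 v 20 a two-sided 5% Fisher test has 7% power for 10% v 20% and 17% for 5% v 20%. If the true rates were 20% on co-administration and 10% on rituximab, co-administration would show a rate no higher than rituximab with probability 25%; for 10% v 5% the probability is 39%.

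**The case against.** Descriptive safety reporting is usual in a small proof-of-mechanism study that declares itself unpowered for pre-defined differences, and tests would detect little. Section 7.4.1.4 defers the AESI analysis to the Reporting and Analysis Plan, which is not at hand and may already contain risk-difference intervals. Sections 9.2.1 and 9.2.2 illustrate sample size and do not limit what is reported. The internal safety review committee sees unblinded data from all arms. All of this stands, and it is why the request is for estimates, stated as descriptive.

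It does not dispose of the point, because the protocol is not silent. Section 9.1 sets a rule against formal comparison for this objective and leaves unclear whether an interval for a difference would breach it.

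Four stronger readings are tempting but not supported:

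- A reader might infer that every between-arm comparison is ruled out. Only formal comparison and testing are excluded; safety tables and graphs by arm remain possible.
- A reader might take Section 2.1 to pose a comparative safety question, since it asks whether treatment "demonstrates a favorable safety and tolerability profile and results in improvements in clinical status" and ends with "mechanistic endpoints in comparison to placebo or rituximab monotherapy". The closing phrase may govern only the improvements. Section 4.1 favours that reading, because it names no comparator for safety and attaches one to the immunological mechanisms. No formal statement of the primary objective names a safety comparator.
- A reader might infer that equal counts will be taken as no added risk. No text says so.
- A reader might set these widths against the 20% stopping rate in Section 5.4.4. That is an absolute rate of specific events in one arm, not a between-arm excess, so the two should not be compared.

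**Conclusion.** The point holds as one about method and clarity. The primary objective is left with by-arm counts, blinded attribution and a one-arm precision statement, although the design randomises the control that would inform the risk the protocol is concerned about. Equal counts at 20 v 20 leave an excess of roughly 13 to 23 points open, and a one-arm interval of 1 to 24% does not show this. The size rests on the planned arm sizes, on illustrative counts of 0 to 3 per arm, and on treating arms as independent binomials without adjustment for strata or follow-up time.

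The contrast with the secondary endpoints is real but should not be overstated: Section 9.4.3 covers the five pairs in Section 9.1, which omit rituximab v placebo.

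The mismatch between Section 3 and Section 9.1 with the synopsis over rituximab monotherapy is separate and minor. Safety summaries cover every dosed subject either way, but the wording should agree.

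**What to change.** Reword Sections 9.1 and 9.4.2 along these lines: no hypothesis tests are performed on safety data; for subjects with at least one SAE, at least one AESI and at least one serious infection, arm incidences and descriptive risk differences are presented with 95% intervals; similar counts do not show absence of added risk. The contrasts would be co-administration minus rituximab, minus belimumab and minus placebo, and belimumab minus placebo.

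Name one interval method, either Newcombe or the Beta(1,1) approach already used in Section 9.2.1, because they differ when events are few (±16 v ±13 points at 0 v 0).

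Add to Section 9.2.1 the expected interval width for the difference at 20 v 20 and 20 v 10. Align the primary objective in Section 9.1 and the synopsis with Section 3.

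The cost is one table and a few sentences. The intervals will be wide and unadjusted, and they will show openly how little a trial of this size can exclude.
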